### **10.1.4 Quality Control and Quality Assurance**

The sponsor will implement the trial-related quality management activities in accordance with ICH GCP guidance and standard operating procedures.

#### **10.1.4.1 Monitoring**

The sponsor has ethical, legal, and scientific obligations to follow this trial in accordance with established research principles, the applicable ICH GCP guidance, and applicable regulatory requirements and local laws. As part of a concerted effort to fulfill these obligations (maintain current personal knowledge of the progress of the trial), the

sponsor's monitors will visit the site during the trial, as well as communicate frequently via telephone, e-mail, and written communications. In addition, all investigators and trial site personnel (including those in charge of blood sampling for clinical laboratory tests) will undergo initial and ongoing training for this particular trial, and this training will be clearly documented.

#### **10.1.4.2     Auditing**

The sponsor's Quality Assurance Unit (or representative) may conduct trial site audits. Audits will include, but are not limited to, IMP supply, presence of required documents, the informed consent process, site operations, delegation of authority and training, and a review of the eCRF with source documents, as applicable. The investigator will agree to cooperate and participate with audits.

Regulatory authorities may inspect the investigator site during or after the trial. The investigator will cooperate with such inspections and will contact the sponsor immediately if such an inspection occurs.

#### **10.1.5     Protocol Deviations**

In the event of a significant deviation from the protocol due to an emergency, accident, or mistake (eg, violation of informed consent process, IMP dispensing or subject dosing error, treatment assignment error, subject enrolled in violation of eligibility criteria or concomitant medication criteria), the investigator or designee will contact the sponsor or designee at the earliest possible time by telephone or via e-mail. The investigator and sponsor (or designee) will come as quickly as possible to a joint decision regarding the subject's continuation in the trial. This decision will be documented by the investigator and the sponsor (or designee) and reviewed by the site monitor.

Any major protocol deviation will be recorded in the source documents and eCRF along with the start date and details of the deviation.

#### **10.1.6     Records Management**

##### **10.1.6.1     Source Documents**

Source documents are defined as records of the results of original observations and activities of a clinical investigation. Source documents will include but are not limited to medical records, electronic data, logs, and recorded data from automated instruments or applications. All source documents pertaining to this trial (except for those related to drug concentration measurement, PGx assessment, and FBR) will be maintained by the trial sites and made available for direct inspection by authorized persons.

Investigator(s)/institution(s) will permit trial-related monitoring, audits, IRB review, and regulatory inspection(s) by providing direct access to source data/documents by authorized persons as defined in the ICF. Documents related to drug concentration measurement, PGx assessment, and FBR (eg, original reports, measurement data, etc) will be retained by the bioanalytical laboratory, PGx laboratory, and biorepository /laboratory related to FBR, respectively. In all cases, subject confidentiality must be maintained in accordance with local regulatory requirements.

#### **10.1.6.2 Data Collection**

During each subject's visit to the site, an investigator or their designee participating in the trial will record information to document all significant observations. At a minimum, these notes will contain:

- Documentation of the informed consent process, including any revised consents;
- Documentation of the investigator's decision to enroll the subject into the trial, the review of all inclusion/exclusion criteria prior to IMP administration, and confirmation of the subject's actual participation in the trial;
- Documentation of baseline and demographic characteristics (eg, age, sex, race, ethnicity, etc);
- The date of the visit and the corresponding Visit or Day in the trial schedule;
- General subject status remarks, including any *significant* medical findings. The severity, frequency, duration, action taken, and outcome of any AEs and the investigator's assessment of relationship to IMP or other drugs used in the clinical trial must also be recorded;
- Any changes in concomitant medications or dosages;
- A general reference to the procedures completed, including dosing and IMP compliance;
- The signature (or initials) and date of the investigator (or designee) who made an entry in the medical record.

In addition, any contact with the subject via telephone or other means that provides significant clinical information will also be documented in the medical records as described above.

Information from medical records and other source documents will be entered by investigative site personnel onto eCRFs in the sponsor's electronic data capture (EDC) system that is 21 CFR Part 11 compliant. Changes to the data will be captured by an automatic audit trail in the EDC system.

Electronic data not entered on eCRF, such as data received from central laboratories and central ECG readers, will be reconciled using key data fields by the sponsor or the CRO with the eCRF data to ensure consistency.

#### **10.1.6.3 File Management at the Trial Site**

The head of the trial site will ensure that the trial site file is maintained in accordance with ICH guidance and as required by applicable local regulations. The trial site will take measures to prevent accidental or premature destruction of these documents.

#### **10.1.6.4 Records Retention at the Trial Site**

The trial site will retain all the trial-related documents and records for the longest of the following 3 periods. However, if the sponsor requires a longer period of archiving, the head of the trial site will consult with the sponsor on the period and procedures of record retention.

- A period of at least 2 years after the date on which approval to market the drug is obtained. However, if the head of the trial site receives notification from the sponsor that development has been terminated or that results of the trial will not be submitted with the approval application, a period of at least 3 years after receipt of such notification.
- A period of at least 3 years after discontinuation or completion of the trial.
- A period of FBR sample storage.

The trial site must not dispose of any records relevant to this trial without either (1) written permission from the sponsor or (2) provision of an opportunity for the sponsor to collect such records. The trial site will be responsible to maintain adequate and accurate electronic or hard copy source documents of all observations and data generated during this trial including any data clarification forms received from the sponsor. Such documentation is subject to inspection by the sponsor and relevant regulatory authorities.

#### **10.1.6.5 Publication Authorship Requirements**

Authorship for any Otsuka-sponsored publications resulting from the conduct of this trial will be based on International Committee of Medical Journal Editors (ICMJE) authorship criteria (<http://www.icmje.org/recommendations>). According to ICMJE guidelines, one may be considered an author only if the following criteria are met:

- 1) Substantial contributions to the conception or design of the work; or the acquisition, analysis, or interpretation of data for the work; AND
- 2) Drafting the work or revising it critically for important intellectual content; AND
- 3) Final approval of the version to be published; AND
- 4) Agreement to be accountable for all aspects of the work in ensuring that questions related to the accuracy or integrity of any part of the work are appropriately investigated and resolved.

All authors must meet the above criteria, and all who qualify for authorship based on the above criteria should be listed as authors.

Investigators or other trial subjects who do not qualify for authorship may be acknowledged in publications resulting from the trial. By agreeing to participate in the trial, investigators or other trial subjects consent to such acknowledgement in any publications resulting from its conduct.

## 10.2 Appendix 2: Clinical Laboratory Tests

The tests detailed in [Table 10.2-1](#) will be performed.

Table 10.2-1 Clinical Laboratory Assessments	
Hematology:	Blood chemistry:
Hemoglobin	ALP
Hematocrit	ALT
RBC count	AST
WBC count (absolute and differential)	Albumin
Platelets	Total bilirubin
Urinalysis:	BUN
Occult blood	Uric acid
Glucose	Serum electrolytes (Na, K, Cl, Ca, Mg, P, bicarbonate)
Microscopic analysis, WBC/RBC counts per high powered field	Cholesterol (total cholesterol, LDL cholesterol, and HDL cholesterol)
pH	Creatinine
Protein	$\gamma$ -GTP
Ketone body	Glucose
Specific gravity	LDH
	Total protein
	Triglyceride
	CPK
	Prolactin
	HbA1c
	Insulin
	Thyroid function test (at screening only):
	TSH and FT 4
	Additional tests:
	Urine (or serum) pregnancy test for females of childbearing potential
	Urine drug screening (amphetamines, barbiturates, benzodiazepines, cannabinoids, cocaine, marijuana, opiates, and phencyclidine)
	Alcohol breath test

ALP = alkaline phosphatase; BUN = blood urea nitrogen; HDL = high-density lipoprotein; LDH = lactate dehydrogenase; LDL = low-density lipoprotein; RBC = red blood cell; WBC = white blood cell;  $\gamma$ -GTP = Gamma-glutamyl transpeptidase.

### **10.3 Appendix 3: Contraceptive Guidance and Collection of Pregnancy Information**

Females of childbearing potential (FOCBP) are females whose menstruation has started and who are not documented as sterile (eg, have had a bilateral oophorectomy, or hysterectomy, or who are postmenopausal). Postmenopausal is defined as being amenorrheic for at least 12 months without any medical cause. Females of non-childbearing potential do not meet the definition of FOCBP.

For males and FOCBP, or their partners, who are sexually active, there must be a documented agreement that the subject and their partner will take effective measures (ie, 2 different approved methods of birth control) to prevent pregnancy during the course of the trial and for 28 days after the last administration of drugs used in the clinical trial.

Unless the subject or their partner is sterile (ie, females who have had a bilateral oophorectomy, have had a hysterectomy, or have been postmenopausal for at least 12 consecutive months; or males who have had a bilateral orchectomy) or remains abstinent during the trial and for 28 days after the last administration of drugs used in the clinical trial, 2 of the following approved methods of birth control must be used: vasectomy, tubal ligation, intrauterine device, birth control pill, condom (all of which are approved in Japan). Any single method of birth control, including vasectomy and tubal ligation, may fail, leading to pregnancy. The contraceptive method will be documented in the source document. Subjects must also agree not to donate sperm or eggs from trial screening through 28 days after the last administration of drugs used in the clinical trial.

Before enrolling males and females in this clinical trial, investigators must review the following information about trial participation as part of the ICF process. The topics should generally include:

- General information
- ICF
- Pregnancy prevention information
- Drug interactions with hormonal contraceptives
- Contraceptives in current use
- Follow-up of a reported pregnancy

Before trial enrollment, males and FOCBP must be advised of the importance of avoiding pregnancy during trial participation and the potential risk factors for an unintentional pregnancy. Subjects must sign the ICF confirming that the above-mentioned risk factors and the consequences were discussed.

A urine or serum pregnancy test for hCG will be performed at screening on all FOCBP. If a urine test is performed and is positive, the investigator will follow-up with a confirmatory serum test.

During the trial, all FOCBP should be instructed to contact the investigator immediately if they suspect they might be pregnant (eg, missed or late menstrual cycle). Male subjects must be instructed to contact the investigator immediately, during the trial, if their partner suspects that they might be pregnant (eg, missed or late menstrual cycle).

If a subject is suspected to be pregnant before she receives the drugs used in the clinical trial, the drug must be withheld until the results of pregnancy tests are available. If the pregnancy is confirmed, the subject must not receive the drugs used in the clinical trial and must not be enrolled in the trial. If pregnancy is suspected while the subject is taking the drugs used in the clinical trial, the drugs must be withheld immediately (if reasonable, taking into consideration any potential withdrawal risks) until the result of the serum pregnancy test is known. If pregnancy is confirmed, the drugs used in the clinical trial will be permanently discontinued in an appropriate manner (eg, dose tapering if necessary for subject safety) and the subject will be withdrawn from the trial. Exceptions to trial discontinuation may be considered for life-threatening conditions only after consultations with the IRE contact (see the title page of this protocol for contact information).

The investigator must immediately notify the sponsor (within 24 hours) of any pregnancy associated with IMP exposure during the trial and for at least 28 days after the last dose of drugs used in the clinical trial, and record the event on the IRE form, etc, and forward it to the sponsor. The sponsor will forward the Pregnancy Surveillance Form(s) to the investigator for monitoring the outcome of the pregnancy.

Protocol required procedures for trial discontinuation and follow-up must be performed on the subject unless contraindicated by pregnancy (eg, x-ray studies). Other appropriate pregnancy follow-up procedures should be considered if indicated. In addition, the investigator must report to the sponsor, on the Pregnancy Surveillance Form(s), follow-up information regarding the course of the pregnancy, including perinatal and neonatal outcome. Infants will be followed for a minimum of 6 months from the date of birth.

A series of horizontal black bars of varying lengths, likely representing data points or categories in a list. The bars are arranged vertically and have irregular, stepped ends, suggesting a list of items with different lengths or values. The lengths of the bars range from approximately 10% to 100% of the page width.

Condition Category	Percentage
All health conditions	85
Mental health conditions	75
Physical health conditions	70
Heart conditions	65
Stroke conditions	60
Arthritis	55
Diabetes	50
Asthma	45
Other respiratory conditions	40
Migraine	35
Headache	30
Other conditions	25

A 10x10 grid of black bars on a white background. The bars are of varying lengths and are positioned in a sparse, non-uniform pattern. Some bars are very long, while others are very short. The grid is composed of 100 individual cells, each containing either a short bar or a long bar, or no bar at all. The overall pattern is irregular and lacks a clear, organized structure.

## 10.5 Appendix 5: Sample Menus of High-fat Meals

Breakfast served before fed-state IMP administration must meet the requirements specified in [Section 5.3.1](#). Sample high-fat menus are shown in [Table 10.5-1](#).

Table 10.5-1 Sample High-fat Menus		
	Meal Components	Amount of Intake
Sample 1	Vacuum-packed white rice	200 g (1 pack)
	Retort pouch curry	1 pouch
	Package of milk	200 mL (1 pack)
	Canned Spam	100 g (approximately half of 1 can)
Sample 2	Vacuum-packed white rice	180 g (1 pack)
	Retort pouch beef stew	1 pouch
	Retort-packed ham	140 g (1 pack)
	Water	150 mL

## **10.6 Appendix 6: Protocol Amendments**

The investigator will not make any changes to this protocol without the sponsor's prior written consent and subsequent approval by the IRB. Any permanent change to the protocol, whether an overall change or a change for specific trial site(s), must be handled as a protocol amendment. Any amendment will be written by the sponsor. Each amendment will be submitted to the IRB, as required by local regulations. Except for "administrative" or "non-substantial" amendments, investigators will wait for IRB approval of the amended protocol before implementing the change(s). Administrative amendments are defined as having no effect on the safety of subjects, conduct or management of the trial, trial design, or the quality or safety of the IMP(s) used in the trial. A protocol change intended to eliminate an apparent immediate hazard to subjects should be implemented immediately, followed by IRB notification within local applicable timelines. The sponsor will submit protocol amendments to the applicable regulatory agencies within local applicable timelines as required.

When the IRB, investigators, and/or the sponsor conclude that the protocol amendment substantially alters the trial design and/or increases the potential risk to the subject, the currently approved written ICF will require similar modification. In such cases, after approval of the new ICF by the IRB, repeat written informed consent will be obtained from subjects enrolled in the trial before expecting continued participation and before the amendment-specified changes in the trial are implemented.

### **10.6.1 Protocol Amendment(s)/Administrative Change(s)**

[REDACTED]

[REDACTED]

[REDACTED]

[REDACTED]

[REDACTED]

[REDACTED]

[REDACTED]

THE JOURNAL OF CLIMATE

The figure consists of a 6x2 grid of horizontal bar charts. The bars are black and vary in length. The first column has shorter bars, while the second column has longer bars. The bars in the second column are consistently longer than those in the first column.

[REDACTED]

[REDACTED]

## List of Abbreviations and Definition of Terms

Abbreviation	Definition
AE	Adverse event
BMI	Body mass index
CGI-I	Clinical Global Impression - Global Improvement
CGI-S	Clinical Global Impression - Severity of Illness
CRF	Case report form
C-SSRS	Columbia-Suicide Severity Rating Scale
CYP2D6	Cytochrome P450 2D6
DIEPSS	Drug Induced Extra-Pyramidal Symptoms Scale
DSM-5®	Diagnostic and Statistical Manual of Mental Disorders Fifth Edition
ICH	The International Council for Harmonisation of Technical Requirements for Pharmaceuticals for Human Use
MedDRA	Medical Dictionary for Regulatory Activities
OD	Orally disintegrating
PT	Preferred Term
QTc	QT corrected for heart rate
QTcF	QT interval as corrected by Fridericia's formula
QW	Quaque (Once) Weekly
SOC	System Organ Class
TEAE	Treatment-emergent adverse event
WHODD	World Health Organization Drug Dictionary

## 1 Introduction

This statistical analysis plan documents in detail the statistical analysis methods planned for Trial 331-102-00151.

## 2 Trial Objectives

To investigate the effect of food on the pharmacokinetics (PK) of a single dose of brexpiprazole once-weekly (QW) formulation at 48 mg in patients with schizophrenia and to confirm safety under those conditions.

[figure not shown]
Table 2-1 Trial Objectives and Endpoints	
Objectives	Endpoints
Primary objective: To investigate the effect of food on PK of a single dose of brexpiprazole QW formulation at 48 mg in patients with schizophrenia	Primary pharmacokinetic endpoint: Geometric mean ratio and two-sided 90% confidence interval of $C_{max}$ , $AUC_{\infty}$ , and $AUC_t$ of brexpiprazole in plasma after administration in a fed state versus administration in a fasting state  Secondary pharmacokinetic endpoints: 
 
Plasma concentrations of brexpiprazole and metabolite [REDACTED]
 
Pharmacokinetic parameters of brexpiprazole and metabolite [REDACTED] in plasma
 

Secondary objective: To confirm safety of the brexpiprazole QW formulation in patients with schizophrenia	Safety endpoints: 
 
Adverse events (AEs)
 
Clinical laboratory tests
 
Vital signs (body temperature, blood pressure, and pulse rate)
 
Physical examination findings
 
Body weight
 
Body mass index (BMI)
 
12-Lead electrocardiography (ECG)
 
Drug Induced Extrapyramidal Symptoms Scale (DIEPSS)
 
Columbia-Suicide Severity Rating Scale (C-SSRS)
 
 Other endpoints: 
 
Clinical Global Impression - Severity of Illness (CGI-S)
 
Clinical Global Impression - Global Improvement (CGI-I)
 
Bowel-movement investigation
 

### 3 Trial Design

### 3.1 Type/Design of Trial

The trial design schematic is shown in Figure 3-1.

This is a multicenter, randomized, open-label, 2-arm, 2-period crossover trial to investigate the effects of food on the PK of brexpiprazole QW formulation in patients with a diagnosis of schizophrenia (295.90) based on the Diagnostic and Statistical Manual of Mental Disorders Fifth Edition (DSM-5®). The trial consists of 2 periods, namely, the screening period and the investigational medicinal product (IMP) administration period (including washout period and follow-up period). The IMP administration period comprises Period 1 and Period 2 to investigate the effects of food on the PK of brexpiprazole QW formulation 48 mg, in which a single oral dose of brexpiprazole QW formulation will be administered at 48 mg in a fasting state or within 10 minutes of finishing a high-fat meal employing a 2-arm, 2-period crossover design. The sample size necessary for the trial assessment is a total of 36 subjects as trial completers.

[figure not shown]
## Figure 3-1 Trial Design Schematic

aBrexipiprazole-naïve subjects will undergo and complete oral administration of brexipiprazole conventional tablet 1 mg (1 mg × 1 tablet) or OD tablet 1 mg (1 mg × 1 tablet or 0.5 mg × 2 tablets) for 2 consecutive days no later than 20 days prior to commencement of brexipiprazole QW formulation administration in Period 1, to verify that they have no allergic reaction or hypersensitivity.

b [REDACTED]

For more information, contact the Office of the Vice President for Research and Economic Development at [contact] or [[contact]](mailto:[contact]).

[REDACTED]

9 

For more information, contact the Office of the Vice President for Research and Economic Development at [contact] or [[contact]](mailto:[contact]).

dThe meal will be a high-fat meal (approximately 900 kcal or more containing approximately 35% or more lipid content). For administration after a meal in Period 1 or Period 2, if the high-fat meal cannot be eaten completely during the period specified in Section 5.3.1 Meals and Dietary Restrictions of the protocol, the date of IMP administration may be postponed once only. The date of IMP administration in Period 1 can be adjusted within a period of 42 days from the start date of screening and, with the date of IMP administration in Period 1 counted as Day 1, the date of IMP administration in Period 2 can be adjusted between Day 30 and Day 36.

### 3.2 Trial Treatments

A single oral dose of two 24 mg tablets of brexpiprazole QW formulation (48 mg as brexpiprazole) will be administered with approximately 150 mL of water in a fasting state (following at least 10 hours of fasting) or within 10 minutes after the completion of a high-fat meal consumed over 20 minutes or less following at least 10 hours of fasting.

### 3.3 Trial Population

Patients at least 18 years of age and below the age of 65 with a diagnosis of schizophrenia based on the diagnostic criteria proposed in the DSM-5®

### 3.4 Trial Visit Window

Data at each time point will be summarized using data at the time point recorded in the case report form (these data will not be summarized at the time of withdrawal or follow-up examination). Unscheduled visit data will not be used. For the criteria of potentially clinically significant laboratory test values, vital signs, body weight, and ECG and the categorical analysis of QT interval as corrected by Fridericia's formula (QTcF) interval to be summarized at any time other than the time points, withdrawal and unscheduled visit data will also be used.

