#### **9.4.2.5      Columbia-Suicide Severity Rating Scale**

The number and proportion of subjects with each C-SSRS item (suicidality, suicidal ideation, suicidal behavior, completed suicide, emergence of suicidal ideation, emergence of serious suicidal ideation, worsening of suicidal ideation, and emergence of suicidal behavior) at each time point will be determined.

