### **9 Safety Analyses**

The safety analysis set will be used for analysis by meal condition (in subjects who receive trial treatment under each meal condition). The baseline value will be the last measurement prior to IMP administration in each period.

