### **9.4 Vital Sign Data**

For each vital sign parameter, descriptive statistics of actual measurements and changes from baseline at each time point will be calculated. Blood pressure and pulse rate measured in a sitting position will be used.

The number and proportion of subjects in whom any measurement after IMP administration in each period up to before IMP administration in the next period (if the IMP is to be administered in the next period) meets the criteria for potentially clinically significant vital signs (Appendix 2) will be determined. A listing of subjects who meet the criteria will be provided.

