### **9.7.3      *Columbia-Suicide Severity Rating Scale***

The number and proportion of subjects with each C-SSRS item (suicidality, suicidal ideation, suicidal behavior, completed suicide, emergence of suicidal ideation, emergence

of serious suicidal ideation, worsening of suicidal ideation, and emergence of suicidal behavior) at each time point will be determined.

The definition for each C-SSRS item other than completed suicide is provided as follows:

- Suicidality: “Yes” to any question of suicidal ideation or suicidal behavior
- Suicidal ideation: “Yes” to any question of suicidal ideation
- Suicidal behavior: “Yes” to any question of suicidal behavior
- Emergence of suicidal ideation: Suicidal ideation is absent at baseline and present after baseline.
- Emergence of serious suicidal ideation: Suicidal ideation is absent at baseline and present with an intensity of 4 or 5 after baseline.
- Worsening of suicidal ideation: Increase in the intensity of suicidal ideation after baseline
- Emergence of suicidal behavior: Suicidal behavior is absent at baseline and present after baseline.

The baseline in this section is the baseline specified in [Section 9](#), not the assessment performed using the “Baseline/Screening Version.” If the response to all the questions on suicidal ideation is negative, the intensity of suicidal ideation will be 0.

The categories of suicidal ideation and suicidal behavior are indicated below.

Suicidal ideation:

1. Wish to be dead
2. Non-specific active suicidal thoughts
3. Active suicidal ideation with any methods (not plan) without intent to act
4. Active suicidal ideation with some intent to act, without specific plan
5. Active suicidal ideation with specific plan and intent

Suicidal behavior:

Actual attempt, interrupted attempt, aborted attempt, preparatory acts or behavior, suicidal behavior

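### SAP 3.4 and 9.7.3 leave suicidality first recorded at a withdrawal or unscheduled C-SSRS assessment out of CT-15, the only C-SSRS summary table

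*SAP*

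**What the plan says.** SAP 3.4 builds each by-time-point summary from the time point recorded in the case report form. It says that "these data will not be summarized at the time of withdrawal or follow-up examination" and adds: "Unscheduled visit data will not be used". One exception follows. It covers the potentially clinically significant criteria for laboratory values, vital signs, body weight and ECG, and the categorical QTcF analysis. It ends with the words "interval to be summarized at any time other than the time points, withdrawal and unscheduled visit data will also be used". C-SSRS is not among the items named, and follow-up data are not readmitted for any parameter.

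SAP 9.7.3 lists the C-SSRS items to be counted and ends: "worsening of suicidal ideation, and emergence of suicidal behavior) at each time point will be determined". Protocol 9.4.2.5 has the same rule. SAP 9.7.3 then defines emergence of ideation without reference to visits: "Suicidal ideation is absent at baseline and present after baseline". For baseline it points to SAP 9: "The baseline value will be the last measurement prior to IMP administration in each period".

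In SAP Appendix 4, CT-15 is the only C-SSRS summary table. Appendix 5 lists the individual answers in PDATA-11.1 to 11.3.

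**The concern.** Emergence and worsening are post-baseline events, so a reader will take CT-15 as the count of subjects who had them under each meal condition. Under the rules as written it counts only what was recorded at scheduled time points. A subject whose ideation or behavior is first recorded when they withdraw, or at an extra assessment prompted by their condition, has no row to appear in. CT-15 could then show no emergent suicidality for a meal condition while the listings show a case, and the reader would have to reconcile the two by hand. Confirming safety is the secondary objective, and C-SSRS is a listed safety endpoint.

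**Working it through.** The plan states no figure to reproduce. The check sets the rules side by side and then bounds the uncounted interval.

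**Is C-SSRS done outside scheduled time points?** Protocol 1.3.2.6 calls for the assessments of Table 1.3-1 at withdrawal. In that table the Period 1 C-SSRS row has 7 post-dose marks (24, 48, 72, 120, 168, 240 and 312 h). The Period 2 row, which also carries the withdrawal and follow-up columns, has 8 marks after baseline. If Period 2 repeats the Period 1 schedule, 8 − 7 = 1 mark lies outside the scheduled time points, which fits the withdrawal column.

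**Does a later scheduled form pick the case up?** Protocol 8.7.5 uses the Since Last Visit version after screening, which asks only about the time since the previous assessment. A case recorded at an unscheduled assessment need not be recorded again. After a withdrawal examination there is no further scheduled treatment-period time point.

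**Is there a rule that moves such data to a scheduled visit?** SAP 10.3 has one, but for plasma concentrations only.

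**What is and is not counted in CT-15:**

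- First yes at a scheduled C-SSRS, subject then withdrawn: counted at that time point.
- No at the last scheduled C-SSRS, first yes at the withdrawal examination: not counted.
- First yes at an unscheduled assessment, no at the next scheduled one: not counted.
- First yes at follow-up: not counted, if C-SSRS is done there.

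**Size of the interval before a withdrawal examination.** Footnote n of Table 1.3-1 limits this examination to the time from dosing to completion of the Day 14 examination. Nominal times from dosing are 0, 24, 48, 72, 120, 168, 240 and 312 h. Successive differences are 24, 24, 24, 48, 48, 72 and 72 h, so the maximum is 72 h. The bound concerns withdrawal examinations only; an unscheduled assessment can fall at any time.

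**The contrast inside the SAP.** For the significance criteria, SAP 9.3, 9.4, 9.6 and 9.7.1 count "any measurement after IMP administration in each period up to before IMP administration in the next period". That window has no visit restriction between doses. SAP 9.7.3 has no counterpart.

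**The case against.** The strongest reply is that nothing is lost. The answers are in PDATA-11.1 to 11.3. Treatment-emergent adverse events are counted from dosing to the next dose with no visit exclusion, deaths enter CT-8.4.1 and CT-9.1, and other serious events enter CT-8.5.1 and CT-9.2. Entry criteria exclude ideation items 4 and 5 and recent suicidal behavior. The trial is sized for 36 completers and has no inferential safety analysis, so listings are a workable source. Most of this stands, and it is why the point is minor. It does not make CT-15 complete. No visible rule turns a positive C-SSRS answer into an adverse event, and Protocol 8.8.2 restricts when worsening of the underlying disease is reported as one.

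A second reply is that only the title of CT-15 is public and the definition of emergence would allow an any-time row. That is possible, but neither SAP 3.4 nor 9.7.3 provides for one.

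Four stronger readings are tempting, and the documents do not support them:

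- A reader might infer that anyone who withdraws because of suicidality is missed. A case first recorded at a scheduled C-SSRS is counted there.
- A reader might infer that much of Period 2 is uncounted because follow-up is excluded. The extracted Table 1.3-1 has lost columns. The C-SSRS row fills its last cell, as DIEPSS and CGI-S do, but it gains only one mark over Period 1, as vital signs, ECG and body weight do. Whether C-SSRS is done at follow-up cannot be confirmed, so no share of time is claimed.
- A reader might scale one missed case against the 36 completers. CT-15 uses dosed subjects by meal condition, and a subject who withdraws before the Period 2 Day 14 blood sample is not a completer.
- A reader might infer that SAP 3.4 also excludes the Period 2 pre-dose C-SSRS. It is a scheduled assessment; the question there is which period it is attributed to.

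**Conclusion.** The point holds and is minor. Taken together, SAP 3.4 and 9.7.3 omit from CT-15 any suicidality first recorded at a withdrawal or unscheduled assessment. This follows from a stated rule, not from missing detail. The effect is confined to the CT-15 counts. Before a withdrawal examination the uncounted interval is at most 72 h between nominal time points. How many subjects this would concern cannot be estimated, because the documents give no event rate. The conclusion assumes that CT-15 is programmed as SAP 3.4 and 9.7.3 are written, and that Period 2 follows the Period 1 C-SSRS schedule.

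**What to change.** Three changes to the SAP:

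1. In 3.4, add C-SSRS to the exception so that withdrawal and unscheduled assessments are used. If C-SSRS is scheduled at follow-up, name follow-up assessments explicitly for C-SSRS, since the present exception does not admit them.
2. In 9.7.3 and CT-15, keep the by-visit rows and add, by meal condition, a row for each item at any time from dosing in the period until dosing in the next. SAP 9.3, 9.4, 9.6 and 9.7.1 already use this window.
3. Add a footnote saying that, under this window, the Period 2 pre-dose C-SSRS counts as a Period 1 outcome and also remains the Period 2 baseline. The window in 9.3 to 9.7.1, read literally, already gives a pre-dose measurement that double role.

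The cost is a short addition to 3.4 and to 9.7.3, one extra block of rows and the footnote. No new data are needed, and the by-visit rows do not change.
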